#### 1.2.2 Early Markers of Response

Two to 3 months are often required to determine if a KS patient is responding to a therapeutic agent. If early markers of response could be established that would allow physicians to determine with a degree of confidence which patients were going to respond, then patients who were not going to respond would be free to pursue other treatment options.

Because of the importance of cytokines, angiogenic factors and growth factors produced in KS, a number of recent KS therapeutic trials examined biologic endpoints to determine if they correlated with clinical response. All the studies to date have looked at isolated biologic endpoints based on a priori predictions regarding KS biology and/or the mechanism of action of the drug being studied. In a trial of oral 9-*cis* retinoic acid in KS, soluble Interleukin-6 receptor (sIL6R) was significantly lower at baseline in responders and IL-6 levels increased in responders. In a study of COL-3, a matrix metalloproteinase inhibitor, VEGF levels were shown to decrease in responders while b-FGF remained unchanged. These reports suggest concentrations of cytokines/growth factors at baseline or changes in the concentrations after being on therapy may be used as predictors of response for KS therapies.

Because of the critical role cytokines/chemokines play in KS development, we hypothesize that these growth factors would be useful biologic endpoints that may be predictive of response. In previous studies investigators had chosen two or three biological endpoints to examine. We will perform a proteomics-based screen for biologic endpoints. The reason for this choice is two-fold: 1) This method allows us to simultaneously examine the majority cytokines and chemokines that are implicated in KS development and, 2) We have limited knowledge of which growth factors may be downstream of the PDGF-R and c-kit pathways in KS.

The PerkinElmer Cytokine Chip is designed to analyze the following cytokines from a sample in a multiplexed fashion:

Table 4. Cytokines detected by PerkinElmer Cytokine Chip					
IL-1 alpha	IL-2s Ra	IL-8	IL-17	MCP-1	sTNF RI
IL-1 beta	IL-3	IL-10	EGF	MCP-2	sTNF RII
IL-1ra	IL-4	IL-12p40	ENA-78	MCP-3	TARC
IL-1R4	IL-5	IL-12p70	FGF-basic	MIG	TNF alpha
IL-1s RI	IL-6	IL-13	G-CSF	MIP-1 alpha	TNF beta
IL-1s RII	IL-6s R	IL-15	GM-CSF	MIP-1 beta	VEGF
IL-2	IL-7	IL-16	IFN gamma	MIP-3 alpha	

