### **2.2 Secondary Objectives**

2.2.1 Evaluation of inhibition of PDGF receptor as determined by immunohistochemistry.

2.2.2 Evaluation of cytokine profiles pre and post imatinib therapy.

2.2.3 Evaluation of pharmacokinetic profile of imatinib and antiretrovirals in HIV patients.

2.2.4 Evaluation of mechanisms of primary and secondary resistance to imatinib therapy.

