- 4.2.6 Biologic Endpoints - Biopsies will be performed at baseline (two), at Day 8 and at time of progression. One biopsy will be performed at baseline and at time of progression or treatment discontinuation for receptor mutation analysis. The DNA from these biopsies will be used to assess exons 12 and 18 in PDGDR  $\beta$ , and exons 11 and 17 in c-kit for mutations that may activate the target receptors or confer resistance to imatinib. If mutations are now found in these exons, we will sequence other exons in which activating mutations have been described. Additionally, RNA from these biopsies will be stored for sequencing cDNAs and accessing expression of downstream targets. These biopsies will be fresh biopsies stored in RNAlator storage media (see Appendix X). Two more biopsies will be performed at baseline and on Day 8 for receptor phosphorylation. These biopsies will assess inhibition of PDGF receptor and will be performed on each specimen. These biopsies will be fixed in 10% formalin (see Appendix X). Serum and plasma specimens for cytokine profiles will be taken at baseline, Day 8 and Day 29 (see Appendix XI). DNA and RNA from PBMCs in these specimens will be stored. The DNA will be used to determine if PDGF-R and c-kit mutations are present in circulating PBMCs, which are infected with KSHV or are restricted to the KS lesions. The RNA will be used for accessing the effect of PDGF-R and c-kit inhibition on the expression of cytokines and other potential downstream targets.
- 4.2.7 Pharmacokinetics - The first 12 patients will have PK sampling performed on Days 1 and 15. Samples will be collected on both days on the following schedule: 0 (immediately prior to patient taking meds for that day), 0.5, 1, 2, 3, 4, 8 and 24 (immediately prior to the next day's dose) hours (see Appendix XII). These data will be compared with historical PK data acquired at the same time points in normal volunteers.

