## 12.0 STATISTICAL CONSIDERATIONS

### 12.1 Sample Size Estimation

The response rate (CR + PR) to imatinib in the pilot study is 50% to date. It is well known that some patients have regression of their KS after beginning HAART therapy. In order to minimize the effect of HAART being a potential confounding factor in response rates, recent studies have required patients on HAART to be on stable regimens for 12 weeks prior to initiation of treatment. Recent results from two placebo-controlled studies suggest as many 20% of responses in KS clinical trials may be delayed responses to HAART alone.[19, Walmsley, 1999 #136] Simon's two-stage design will be used to test the null hypothesis that the response rate (CR + PR) is 20% against the alternative that it is 50% at the one-sided 0.05 significance level with power of 0.90. Ten patients will be enrolled in the first stage. If no more than two patients respond, then the study will be stopped. If at least three patients respond, then the study will enroll up to a total of 22 patients. If no more than seven patients respond, the drug will be considered ineffective. If at least eight patients respond, the null hypothesis will be rejected in favor of the alternative hypothesis. The probability of early termination of the study is 0.68.

In our original estimate, we assumed a drop out rate of 10-15% based on our experience in the pilot study and calculated a sample size of 25 patients. However, we have had a higher drop out rate. Consequently, based on a drop out rate of 20-30%, we plan to roll a total of 30 patients to have 22 patients evaluable for response.

In the pilot study, we found that decreasing the dose of imatinib by 33% (600 mg/day to 400 mg/day) dramatically decreased the incidence of AEs. This dose reduction should reduce the steady state concentration of imatinib and its metabolite by 1 standard deviation of steady state plasma concentration, assuming constant clearance. This observation suggests a change in the plasma concentration imatinib and/or its metabolite of 1 standard deviation would be significant in our patient population. Based on this assumption, a PK sampling of 12 patients will provide a power of 88% to detect a 1 standard deviation change in the steady state level of imatinib and its metabolite with a type I error of 0.05 using a two-sided paired t-test.

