### 12.2 Statistical Analysis Plan

Summary statistics will be used to describe the study population (such as ranges, medians of age, gender, baseline performance characteristics). The binomial and its exact 95% confidence interval will be used to estimate clinical response rate. A two-sided one-group chi-square test will be performed to detect a 50% response rate. Due to a small sample size, exact logistic regression may be used to evaluate the effect of baseline characteristics and other covariates with the clinical response. To evaluate inhibition of PDGF receptor, we will

correlate the presence or absence of c-kit and or PDGF-R mutations with clinical response to imatinib by performing chi-square tests or Fisher's exact tests. The cytokine/chemokine profile at baseline, 1 week and 4 weeks after of imatinib therapy will be analyzed using the proteomics approach. The concentration of each cytokine from the samples will be estimated. Friedman's test will be used to evaluate changes between time points with respect to cytokine levels. If a significant difference is detected, the Wilcoxon rank sum test will be used for pairwise comparisons. Exact logistic regression analysis will be used to detect any correlation between baseline concentrations and clinical responses. PK parameters including AUC,  $C_{max}$  and elimination half-life of imatinib will be estimated in the first 12 patients. PK parameters including AUC,  $C_{max}$  and elimination half-life of selected antiretrovirals may be estimated in selected patients. Summary statistics will be used to describe PK results. The incidence of specific AEs will be summarized by severity grade. The binomial proportion and its 95% confidence interval will be used to estimate the proportion of patients who experience an AE of severity Grade 3 or higher. The proportions of primary and secondary resistance to imatinib therapy will be estimated. Chi-square tests or Fisher's exact tests will be used to evaluate associations between c-kit and PDGF-R mutations with resistance to imatinib therapy.

Cluster analyses are planned for the real-time QPCR data. To evaluate the associations between single genes and response, categorical data analysis methods are proposed. If feasible, a multivariate model relating gene expression to response will be performed.

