## **APPENDIX XI: CYTOKINE PROFILES ANALYSIS**

### **A. METHODOLOGY**

In this study we will examine the patient cytokine profiles at baseline, Day 8 and Day 29. Plasma samples will be assayed using the PerkinElmer cytokine chip as described in the preliminary data. As noted the standards on the cytokine chip are analyzed by point-to-point linear regression and concentrations of experimental samples are estimated from these standard four-point curves. Thus the chip should be considered a semi-quantitative assay and all cytokines/chemokines that appear to be potential predictors will be confirmed by ELISA.

The concentrations of cytokines that are found to be potential predictors by single variant analysis will be determined using commercially available ELISAs. R&D Systems (Minneapolis, MN) produces colorimetric sandwich ELISAs that correspond to the cytokines and chemokines on the cytokine chip. Depending on the ELISA, the intra-assay precision has a CV of 3 to 14 percent and the inter-assay precision has a CV of 7 to 14 percent. The concentrations determined by ELISA will then be analyzed by single variant and multivariate analysis to determine if there is any correlation between concentration at baseline or changes in concentrations after treatment and clinical response.

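### Section 12.2 follows Friedman's test on repeated cytokine samples with the Wilcoxon rank sum test, which is for independent samples; the pairwise step should be a paired test (minor, probably a slip for signed-rank)

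*Combined protocol and SAP*

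**What the plan says.** Secondary objective 2.2.2 reads: "Evaluation of cytokine profiles pre and post imatinib therapy". Section 4.2.6 sets the sampling: "Serum and plasma specimens for cytokine profiles will be taken at baseline, Day 8 and Day 29". Appendix XI (A. Methodology) repeats it: "In this study we will examine the patient cytokine profiles at baseline, Day 8 and Day 29". The trial has a single treatment arm (Schema), so these are three measurements on each patient.

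Section 12.2 describes the same three time points: "The cytokine/chemokine profile at baseline, 1 week and 4 weeks after of imatinib therapy will be analyzed using the proteomics approach". It then gives two steps. The first is: "Friedman's test will be used to evaluate changes between time points with respect to cytokine levels". The second is: "If a significant difference is detected, the Wilcoxon rank sum test will be used for pairwise comparisons". Neither the signed-rank test nor any other paired follow-up for the cytokines is named anywhere in the documents.

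**The concern.** Friedman's test ranks each patient's three values within that patient. The rank sum test pools the values from two time points and treats them as two unrelated groups, so it discards the pairing that the previous sentence relied on.

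Nothing suggests that the pairwise step was meant for independent groups such as responders and non-responders. It is conditional on a test of time points, and the relation of baseline levels to response has its own method in Section 12.2, exact logistic regression.

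At stake is whether a cytokine found to change can be said to have changed by Day 8, by Day 29, or between the two. If the follow-up test is too weak, a significant Friedman test may be followed by no significant pair, and the timing stays unresolved.

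**Working it through.** **Inputs from the documents.** Three time points, hence three pairs per cytokine. 22 patients evaluable for response and 10 in the first stage (Section 12.1), where the rule is: "If no more than two patients respond, then the study will be stopped". Table 4 in Section 1.2.2 lists 41 cytokines (seven rows of six, less one empty cell).

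**Assumptions, because the documents are silent.** Two-sided 5% per test; complete triples; normal data with unit SD; a common within-patient correlation ρ; equal shifts at Day 8 and Day 29. The plan states no power or size for the cytokine tests, so there is no figure of its own to reproduce.

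**Direction of the error.** A difference between two time-point means has variance 2σ²(1−ρ)/n. An independent-samples test in effect uses 2σ²/n. Its real size is therefore roughly 2Φ(−1.96/√(1−ρ)):

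- ρ = 0.3: 2Φ(−2.34) ≈ 1.9%
- ρ = 0.5: 2Φ(−2.77) ≈ 0.6%
- ρ = 0.7: 2Φ(−3.58) ≈ 0.03%

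Simulating the exact rank sum test with 22 patients gives 2.2%, 0.8% and 0.1%, and 4.9% at ρ = 0. The signed-rank test stays near 4.6% throughout.

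**Power after the Friedman gate.** This is the joint probability that Friedman's test and the Day 29 versus baseline test are both significant, with 22 patients and ρ = 0.5:

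| Shift | Rank sum | Signed-rank |
|---|---|---|
| 0.5 SD | 25% | 41% |
| 0.75 SD | 67% | 81% |
| 1 SD | 94% | 97% |

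At ρ = 0 the two tests are level: 19 vs 19%, 47 vs 46% and 76 vs 75%. With 10 patients and ρ = 0.5 the figures are 7 vs 16%, 22 vs 37% and 46 vs 64%.

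**Friedman significant but no pair significant.** The joint probability is the chance that this happens for a given cytokine. The conditional one is the share among significant Friedman tests.

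| Patients, ρ, shift | Rank sum, joint | Rank sum, conditional | Signed-rank, conditional |
|---|---|---|---|
| 22, 0.3, 0.5 SD | 5% | 14% | 2.5% |
| 22, 0.5, 0.5 SD | 13% | 26% | 1.4% |
| 22, 0.7, 0.5 SD | 34% | 47% | 0.4% |
| 10, 0.5, 0.5 SD | 11% | 48% | 4.5% |
| 10, 0.5, 0.75 SD | 14% | 31% | 2% |
| 10, 0.5, 1 SD | 11% | 16% | 0.6% |

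With signed-rank the joint probability is about 1% or less in every row. The two columns agree through the power of Friedman's test. With 22 patients and ρ = 0.5 that power is 48.9%, and 0.26 × 48.9% ≈ 13%. With 10 patients it is about 22% at 0.5 SD, and 0.48 × 22% ≈ 11%. Figures near these may move by about one point between simulation runs.

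**False claims when nothing changes.** With 22 patients and ρ = 0.5, a Friedman-gated false claim in any pair occurs for about 1.2% of cytokines with rank sum and 3.9% with signed-rank. Over the panel that is 41 × 1.2% ≈ 0.5 against 41 × 3.9% ≈ 1.6 expected false claims.

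**The case against.** The strongest reply is that this is a wording slip. The sentence before it names a related-samples test, and the pharmacokinetic power statement in Section 12.1 uses a paired t-test, so the authors plainly know when data are paired. That is probably right, but it does not dispose of the point: rank sum is a real test that runs on these data without error and returns a plausible p-value.

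The second reply is that little depends on this step, and that stands. Friedman's test still answers whether a cytokine changed. The regression of response on baseline levels and the ELISA confirmation (Section 1.2.2 and Appendix XI) do not use it. The chip is described as semi-quantitative in any case.

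The third is that the size of the loss is assumed, not documented. That also stands. The loss runs from nothing at zero correlation to 40 points (26 vs 66%) at ρ = 0.7 and 0.5 SD. Ties, values below detection and missing time points are not modelled.

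Two stronger readings are tempting and not supported:

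- A reader might infer that the wrong test produces spurious cytokine findings. With zero or positive correlation it does not. Only at negative correlation, which is unlikely for repeated measures, would its size exceed 5%: about 8% for the test alone at −0.3, with the Friedman-gated rate still near 4%.
- A reader might take 48% as the chance, with 10 patients, that a cytokine shows a significant Friedman test and no significant pair. That figure is conditional on a significant Friedman test, and the chance itself is about 11%.

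**Conclusion.** The named test is wrong for the design as written, and nothing elsewhere in the documents corrects it. The point is minor. It touches one part of secondary objective 2.2.2, namely which time points differ. The primary response analysis and the sample size are untouched.

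The material loss needs positive within-patient correlation together with a small to moderate shift or few patients. With 22 patients and a 1 SD shift it is only about 3 points at ρ = 0.5. All sizes rest on the normal, complete-data model and the assumed correlations and shifts; the mismatch itself rests only on the text.

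**What to change.** In Section 12.2, replace 'Wilcoxon rank sum test' with 'Wilcoxon signed-rank test', applied to the within-patient differences Day 8 minus baseline, Day 29 minus baseline and Day 29 minus Day 8. Another paired follow-up to Friedman's test would also remove the mismatch; signed-rank is the smallest change. It should be made before the cytokine data are analysed.

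The cost is one phrase, with no new samples, visits or patients. There are two downsides. Gated false claims per cytokine return towards nominal but stay under 5%, as shown above; Section 12.2 names no multiplicity control across the panel, which is a separate matter. If the correlation is near zero, the pairwise test alone may lose about 3 points of power with normal data (66 to 63% at 0.75 SD) and up to about 8 with strongly skewed raw concentrations (66 to 58%). After the Friedman gate these losses shrink to under 1 point and at most 3 points.

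### The 41-cytokine and single-gene screens have no significance level or error control across tests, and ELISA on the same patients confirms a measurement, not a predictor of response

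*Combined protocol and SAP*

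**What the plan says.** Section 1.2.2 describes a proteomic screen for early markers of response, and its Table 4 lists the chip's analytes. Section 12.2 gives the tests. For change across baseline, week 1 and week 4: "Friedman's test will be used to evaluate changes between time points with respect to cytokine levels". Pairwise tests follow only where that result is significant. For prediction: "Exact logistic regression analysis will be used to detect any correlation between baseline concentrations and clinical responses". For the viral transcripts: "To evaluate the associations between single genes and response, categorical data analysis methods are proposed". Cluster analyses and, if feasible, a multivariate gene model are also planned.

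Appendix XI, part A, shows that cytokines are selected one at a time: "The concentrations of cytokines that are found to be potential predictors by single variant analysis will be determined using commercially available ELISAs". Its reason for the second assay is that "the chip should be considered a semi-quantitative assay and all cytokines/chemokines that appear to be potential predictors will be confirmed by ELISA". The ELISA values are then analysed again, singly and jointly, "to determine if there is any correlation between concentration at baseline or changes in concentrations after treatment and clinical response".

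Section 12.1 gives 0.05 for the response-rate test and for the pharmacokinetic t-test. Neither Section 12.2 nor Appendix XI gives a level for the cytokine or gene screens, a definition of the family of tests, a false-discovery rule, cross-validation or a validation cohort.

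**The concern.** A screen of many markers in about 22 patients will usually produce some small p-values when no marker is related to response. The plan does not say which results would count as positive or how many tests stand behind them, so a reader of the final report could not judge a reported marker.

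The ELISA step makes this more serious. Part B of Appendix XI has each specimen split into two tubes, one shipped and one kept at the site, and no other patients or samples are named. The natural reading is that ELISA is run on the trial's own samples and related to the same outcomes. A chance imbalance between responders and non-responders would then still be present at the second assay.

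The possible use of these markers is set out in Section 1.2.2: patients unlikely to respond could turn to other treatment sooner. A chance marker described as confirmed would be a poor basis for that.

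**Working it through.** **Inputs**
- Cytokines: Table 4 has six rows of 6 and one row of 5, so 6 × 6 + 5 = 41, all distinct.
- Patients: 22 evaluable (Section 12.1), or 10 if the trial stops at stage 1.
- Significance level for the screens: not stated. I assume two-sided 0.05 and show 0.01 and 0.10.
- ELISA inter-assay CV: 7-14% (Appendix XI); 14% used.
- Number of KSHV transcripts: not given.

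**The plan's own figures.** No error rate is stated for the screens. The design that fixes the number of patients does reproduce. Early termination at a 20% response rate is P(X ≤ 2 of 10) = 0.107 + 0.268 + 0.302 = 0.678 (stated 0.68). The two-stage rule has one-sided error 0.049 (stated 0.05) and power 0.902 (stated 0.90).

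**Expected false positives in one family of 41 with no real effect.** Expected number = 41 × level, whatever the correlation. If the tests are independent, P(at least one) = 1 − (1 − level)^41.

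| Level | Expected | P(at least one), independent |
|---|---|---|
| 0.01 | 0.41 | 33.8% |
| 0.05 | 2.05 | 87.8% |
| 0.10 | 4.10 | 98.7% |

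There are two such families: change over time, and baseline level against response. If baseline and the two changes (Day 8, Day 29) were all tested against response, there would be 3 × 41 = 123 tests, with 123 × 0.05 = 6.15 expected.

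**Correlated cytokines.** I simulated 22 patients with 8 or 11 responders and no true predictor, using a t-test on the log scale in place of exact logistic regression. Without assay noise, the chance of at least one hit at 0.05 is about 88%, 76% and 49-51% at correlations of 0, 0.3 and 0.6. With chip noise added (CV 20% or 50%), the correlated settings range from 52% to 84%. The expected count stays near 2 throughout.

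**ELISA in the same patients.** With between-patient log SD of 0.5 or 1.0, chip CV of 20% or 50% and ELISA CV of 14%, 30-78% of chance chip hits remain significant on ELISA. That leaves 0.6-1.6 false predictors per trial on average. In new patients about 5% would remain significant.

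**Genes.** The number of tests is unknown, and categorical tests are discrete at this size. Fisher's exact test on a median split of 22 patients, run at nominal 0.05, has a true size of 0.024 with 8 responders and 0.009 with 11. I therefore quote no expected count for genes.

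**Cost of stricter rules.** The chance of detecting one true 1 SD marker is 57-61% at raw 0.05. It falls to 16-19% at a Benjamini-Hochberg q of 0.10, 23-28% (up to 29% in one run) at q of 0.20, and 10-12% under Bonferroni (0.05/41 = 0.00122).

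**The case against.** The strongest reply is that this is discovery work in a small phase II trial and the documents treat it so. The cytokine objective in Section 2.2 is only to evaluate profiles before and after therapy. Section 1.3 speaks of potentially developing predictors, and Appendix XI of potential ones. The viral assays are described as research tests not to be used for clinical decisions. No treatment or stopping rule depends on these markers. The pairwise cytokine tests are also gated by the Friedman result, and the ELISA is justified by the chip's limited precision, which is a measurement reason.

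Most of this stands and limits the consequence. It does not close the gap. The gating works within a cytokine, not across the 41. The research-only caveat covers the HHV-8 assays, not the cytokines. Clustering and a multivariate model do not control the error rate of the single-gene tests. The ELISA values are re-tested against response, so the step does more than check the assay.

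Several stronger readings are tempting, but the documents do not support them:
- That the plan screens at 0.05. It states no level here; 0.05 is my assumption.
- That ELISA cannot remove chance hits. It removed 22-70% of them in the simulation, those arising from chip noise.
- That all false positives would be false predictors. A false positive on the Friedman test is a false claim of change over time, not of prediction.
- That the ELISA problem extends to genes. ELISA applies to cytokines only.

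A further fair objection is that admitting cytokines to ELISA only on adjusted values would lose most moderate true markers at the discovery stage. The power figures bear this out, and the fix does not ask for it.

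**Conclusion.** The point holds for a secondary analysis. The plan screens 41 cytokines in two ways, plus an unstated number of single genes, with no significance level and no error control across tests. At an assumed two-sided 0.05, about two false positives are expected in each cytokine family. The expected count does not depend on correlation; the chance of at least one does. The correlation and noise settings behind the 50-85% range are mine, since the documents give none apart from the ELISA precision.

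That ELISA uses the same patients is an inference from the split specimens and the absence of any other named source, but no other reading fits the text. On that reading, agreement by ELISA shows that the chip measured the cytokine adequately, not that the cytokine predicts response. The primary response-rate conclusion is untouched, so this is a cheap improvement and not a flaw in the design.

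**What to change.** In Section 12.2:
- Define three families: 41 change tests, 41 baseline-against-response tests, and the single-gene tests.
- State the significance level and the adjusted threshold.
- Report the number of tests done in each family, with Benjamini-Hochberg adjusted values beside the raw p-values.
- Call a marker a predictor of response only if it passes on the adjusted value. Describe any other hit as hypothesis-generating and needing validation in new patients.
- If changes in concentration are also tested against response, as Appendix XI allows, count those tests too.

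In Appendix XI, state that ELISA confirms the measurement and not the association with response. Entry to ELISA may stay on raw p-values, so no candidate is lost at that stage.

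The cost is a few sentences and a few lines of code, with no added patients, samples or assays. The downside is that fewer markers can be claimed from this trial alone.
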